Concomitant medications/treatments	
Prohibited drugs/treatments
 
The following drugs/treatments are prohibited during the study period. If any of the following treatment is started after the first dose of study drug on D1, the study treatment must be early terminated:

	
 • Dupilumab or any anti-il-4r α or IL-13 antibodies; • Topical PDE-4 inhibitors or JAK inhibitors; • Systemic treatment with corticosteroids or other immunosuppressive and/or immunomodulatory agents such as cyclosporine, mycophenolate mofetil, azathioprine, methotrexate or oral JAK inhibitors; • Cell depletion agents (e.g., rituximab) or other biological agents; • Other investigational drugs (non CBP-201) or treatments. 
The following treatments are also prohibited during the study period:
 
 • Initiation of SIT or dose up-regulation; • (Attenuated) live vaccine; • Topical corticosteroids (TCS) or TCI; • Phototherapy (NBUVB, UVB, UVA1, PUVA), sunbed or any other LED therapies; • Bleaching baths more than 2 times a week; • Any drug (except mild emollients) that may interfere with the evaluation of efficacy results or affect the evaluation of AD severity. 
Permitted drugs/treatments
 
AD is a chronic recurrent skin disease characterized by periodic aggravation or gradual deterioration of symptoms. If medically necessary (i.e. in order to control intolerable AD symptoms), the investigator can provide patients with rescue therapy for AD by using drugs or treatment regimens that were originally prohibited at their own discretion. According to the investigator's judgment, AD aggravation or deterioration of symptoms which requires drugs or treatments originally prohibited by the protocol for rescue therapy will be defined as "AD recurrence" event, and the onset and duration of these events will be recorded as AE according to the site of attack.
 
Note: The investigator should limit the first-step rescue therapy to topical drugs (TCS or TCI) as far as possible. Only patients who do not respond adequately after at least 7 days of topical medication can be upgraded to systemic medication or other treatments. If a subject receives systemic corticosteroid or non-steroid systemic immunosuppressive/immunomodulatory rescue therapy, the study drug administration will be stopped immediately. (refer to Section 8.2 for details)
 
Other drugs that are permitted may include:
 
 • Emollients (as the background treatment of this study, at least 7 days before baseline, all subjects need to use mild emollients at least twice a day, and continue to use them throughout the study period. During the screening period or the study period, subjects cannot start using prescription emollients or emollients containing additives. However, if a subject has already started using these emollients before the screening visit, he/she needs to continue using them at a stable dose throughout the study period. If the subject is intolerable to the emollients provided uniformly by the sponsor during the screening period, he/she can change to the emollient of this kind used previously, but it must be used at a stable dose for at least 7 days before baseline and during the study period.); • Basic skin care (cleansing and bathing);

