4.4.2. Phase I Multiple Ascending Dose Study

CBP201 was evaluated in a multiple ascending dose (MAD) study in adult patients with AD [30] (Connect study CBP-201AU002). In this randomized, double-blind, placebo-controlled, multiple ascending dose study, 31 moderate to severe AD patients aged 20 to 65 were enrolled at 13 study sites in Australia and New Zealand. The patients received CBP-201 (SC, 75 mg, 150 mg or 300mg) or matching placebo once a week for 4 consecutive weeks. About 10 patients were randomly enrolled in each dose group and received CBP-201 or placebo treatment in a ratio of 4:1.

In general, CBP-201 had good safety and tolerability when the dose of subcutaneous injection was up to 300mg. No SAE, life-threatening TEAEs, or deaths were reported in the study, and no TEAEs that led to discontinuation of the study were reported. No clinically significant injection site reactions were reported as AEs. The most common AEs during the study period were deterioration of AD (26.1% in the combined CBP-201 treatment group and 37.5% in the placebo group), headache, and upper respiratory tract infection. Most TEAEs were mild.

The number and severity of TEAEs and treatment-related TEAEs did not increase with the increase of CBP-201 dose levels. There were no clinically significant (CS) or study treatment-related changes in vital signs, ECG parameters, or physical examination results.

At the doses of 150 mg and 300 mg, CBP-201 administration for 4 weeks could quickly improve EASI, IGA and PP-NRS. On Day 29, 87.5% (7/8 cases) of the patients in the 150 mg group had a 50% reduction in EASI score (EASI-50), and 100% (7/7 cases) of the patients in the 300 mg group achieved EASI-50, while only 37.5% (3/8 cases) of the patients in the placebo group achieved EASI-50. For IGA, 50.0% (4/8 cases) of the patients in the 150mg group, 42.9% (3/7 cases) in the 300 mg group, and only 12.5% (1/8 cases) in the placebo group had an IGA score of 0-1 (clearance, basic clearance). The average weekly PP-NRS severity was decreased by 41.0% and 52.8% in the CBP-201 150 mg group and 300 mg group, respectively, and by 22.8% in the placebo group. On Day 29, the P-NRS response rates (decreased by >3 points) in the 150 mg (50%, 4/8) and 300 mg groups (57%, 4/7) were higher than that in the placebo group (25%, 2/8).

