The safety profile of CBP-201 in this study was generally comparable to that of placebo, with no clinically relevant differences observed between treatment groups. CBP-201 treatment

groups and placebo had a similar incidence of TEAEs, SAEs, and TEAEs leading to discontinuation. The most common TEAEs in the CBP-201 dose groups were atopic dermatitis (15%) and headache (5%); all other TEAEs were reported for $\leq 2\%$ of CBP-201-treated subjects. Most reported TEAEs were mild to moderate in severity. The proportion of subjects with Grade ≥ 3 TEAEs was higher in the 300 mg Q4W group than the 150 mg Q2W group, 300 mg Q2W group, or placebo group. One subject in the 300 mg Q4W CBP-201 group experienced a fatal (Grade 5) TEAE of cardiac arrest 57 days after last dose of study drug. There were no clinically relevant trends in clinical safety laboratory (hematology, blood chemistry, and urinalysis) values, vital sign values, ECG findings, or physical examination findings across doses or over time for up to 16 weeks of treatment.

Administration of CBP-201 resulted in rapid improvements in EASI, IGA, and PP-NRS at 16 weeks. All doses of CBP-201 met the primary endpoint (LS mean percent change from baseline in EASI at Week 16 versus placebo), with greater reductions observed in EASI in the 300 mg Q2W and Q4W groups. Significant improvements with CBP-201 were also seen for a range of secondary efficacy endpoints, including proportions of EASI and IGA 0/1 responders and change in PP-NRS. The efficacy responses of 300 mg CBP-201 Q2W and Q4W were more consistently greater than 150 mg Q2W when compared to placebo across most outcomes.

ADA/NAb results

In the 150 mg Q2W dose group, 8 subjects tested positive for ADA. Five of these subjects tested positive at a single timepoint only, either in the middle of the time course (transient, n = 2) or at only the final timepoint (indeterminate, n = 3). Three subjects had persistent ADA, testing positive at two or more consecutive timepoints. Titers were low, with all titers <1000 . Six subjects were positive for Nab.

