	
factors, or other treatments the patient received, etc.) explain the AE more reasonably than the study drug;
 
• The AE does not disappear or lessen after the drug is stopped or the dose is reduced (if applicable), or the situation is unclear;• The AE does not recur after re-administration, or the situation is unclear.
Not related	
• There is no reasonable temporal sequence between the occurrence of AE and the medication, or;• The AE has other evidence reasons (e.g., the patient's preexisting disease, environmental or toxic factors, or other treatments the patient received, etc.).
Indeterminable	
• The above information is unclear, and the investigator believes that it cannot be judged based on the existing information, and the investigator cannot obtain further follow-up information.

Serious Adverse Event (SAE)

An event will be considered an SAE if the following situations occur. See Section 10.1.2 of the protocol for definition of SAE. SAEs will be judged by investigators on CRF.

- Leading to death;
- Life-threatening: The investigator determines that the patient is at immediate risk of death when the event occurs. This definition does not include events that may lead to death if it is assumed to be more serious;
- Requiring hospitalization or prolongation of the original hospital stay;
- Leading to permanent or major disability or incapacitation (i.e., significant impairment of the subject's activities of daily living);
- Including congenital abnormalities or birth defects in the offspring of the patient;
- Significant medical events: According to the medical judgment of the investigator, other significant medical events that may endanger the patient and may require medical or surgical intervention to prevent one of the above outcomes.

Adverse Event of Special Interest (AESI)

AESIs in the study include: Conjunctivitis, keratitis, anaphylactic reaction, injection site reactions which persist over 24 h, AST/ALT increased $> 5 \times$ ULN, parasitic and opportunistic infection, pregnancy and symptomatic overdoses.

AEs leading to treatment discontinuation

In the study, action taken with study drug is drug discontinued or the subject will be withdrawn from treatment in response to these AEs.

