7.5.2. AEs

AEs will be analyzed based on the SS1 and SS2. Subjects who have received at least one dose of the study drug will be analyzed based on SS3.

AEs will be coded using MedDRA.

The occurrence of overall AEs will be summarized to generate summary tabulations of TEAEs. TEAEs of special interest and drug-related AESIs will be summarized. The numbers of subjects with various AEs, numbers and incidences of events will be calculated. The number of subjects with various AEs, the number of events, the incidence and annual incidence of events will be calculated based on SS3.

AEs, drug-related AEs, SAEs, AESIs, AEs leading to death, AEs leading to treatment discontinuation, injection site AEs, CTCAE grade 3-5 AEs, AEs with an incidence of $> 5\%$, and AD recurrence-related AEs will be tabulated.

The incidences of the following TEAEs will be summarized by SOC and PT, the numbers of subjects with various AEs, and the numbers and incidences of events will be calculated. They will be ranked in descending order of total number of subjects by SOC and PT. In addition, annual incidences of TEAEs, treatment-emergent SAEs, treatment-emergent AESIs, drug-related AEs, drug-related SAEs will be calculated by SOC and PT based on SS3.

- 1) TEAEs;
- 2) Drug-related AEs;
- 3) SAEs;
- 4) Drug-related SAEs;
- 5) AEs leading to death;
- 6) AEs leading to treatment discontinuation;
- 7) AEs leading to treatment interruption;
- 8) AESIs;
- 9) Drug-related AESIs;
- 10) Injection site AEs;
- 11) CTCAE grade 3-5 AEs;
- 12) AEs with an incidence of $> 5\%$;

In addition, the incidences of TEAEs, AESIs, and injection site AEs will be summarized by CTCAE Grade, correlation with study drug, SOC and PT, and the number and percentage of subjects will be calculated.

A subject with an AE of the same SOC and PT more than once will have that event counted only once within each SOC and PT.

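### AD flares needing rescue count as AEs and stay in the overall TEAE total; no placebo comparison without them is planned

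*Protocol*

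**What the plan says.** **Recording rule.** Protocol 8.2.2 and the synopsis define AD recurrence as a worsening that, in the investigator's judgement, needs otherwise prohibited treatment as rescue. They add that "the onset and duration of these events will be recorded as AE according to the site of attack".

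**Efficacy role.** The number of recurrences and of subjects with recurrence are efficacy endpoints (protocol 9.5.1). SAP 7.4.4 compares them between arms by chi-squared test.

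**Safety totals.** SAP 7.5.2 says "The occurrence of overall AEs will be summarized to generate summary tabulations of TEAEs". It then says "The incidences of the following TEAEs will be summarized by SOC and PT" and lists twelve categories, including any TEAE, drug-related, grade 3-5, discontinuation and interruption. No category excludes AD recurrence, and protocol 12.8 has no exclusion either. SAP 7.5.2 also says "AD recurrence-related AEs will be tabulated", but this output is not among the twelve categories.

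**Discontinuation.** Protocol 8.2.2 states: "If a subject receives systemic corticosteroid or non-steroid systemic immunosuppressive/immunomodulatory rescue therapy, the study drug administration will be stopped immediately". SAP 4.2.2 defines AEs leading to discontinuation as those where "action taken with study drug is drug discontinued or the subject will be withdrawn from treatment in response to these AEs". It makes no exception for flares.

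**The concern.** Safety and tolerability is the first secondary objective, and Stage 1 is the only part of the trial with a concurrent placebo arm. An effective drug should reduce flares. If it does, counting flares as TEAEs adds lack of effect to the placebo arm's safety totals, and an excess of other events on CBP-201 looks smaller in the overall row.

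That row matters in practice. Protocol 4.4.4 describes the safety of the earlier Phase 2b study by saying that TEAEs, SAEs and TEAEs leading to discontinuation were of similar incidence on CBP-201 and placebo. In that study AD was the most common TEAE on CBP-201 (15%, against 5% for headache and at most 2% for any other term).

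**Working it through.** The plan gives no figure for this effect, so the size below is an illustration.

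**1. What is known about flare rates by arm.** Protocol 4.4.2 reports "deterioration of AD (26.1% in the combined CBP-201 treatment group and 37.5% in the placebo group" in the multiple-dose study. It had 31 patients, and the efficacy results show 8 on placebo, leaving 31 − 8 = 23 on CBP-201. The percentages reproduce as 6/23 = 26.1% and 3/8 = 37.5%, with the counts inferred. Fisher's exact test gives p = 0.66. These are AEs of AD worsening in a study of four weekly doses, not recurrences needing rescue over 16 weeks. For Phase 2b only the 15% on CBP-201 is given; the placebo rate is not.

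**2. Effect on the overall total.** Assume that flares and other TEAEs are independent within an arm:

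total = 1 − (1 − non-AD rate) × (1 − AD rate)

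The non-AD rates are assumed, with a true 10-point excess on CBP-201. AD rates are 26.1% and 37.5%.

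| Non-AD, CBP-201 v placebo | Total on CBP-201 | Total on placebo | Apparent difference |
|---|---|---|---|
| 40% v 30% | 1 − 0.60 × 0.739 = 55.7% | 1 − 0.70 × 0.625 = 56.2% | −0.6 points |
| 50% v 40% | 1 − 0.50 × 0.739 = 63.1% | 1 − 0.60 × 0.625 = 62.5% | +0.6 points |
| 60% v 50% | 1 − 0.40 × 0.739 = 70.4% | 1 − 0.50 × 0.625 = 68.8% | +1.7 points |

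With AD at 15% on CBP-201 and an assumed 25% on placebo, the same three cases show +1.5, +2.5 and +3.5 points. With an assumed 30% on placebo they show −2.0, −0.5 and +1.0.

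**3. The reverse question: what could equal totals hide?** Setting the two totals equal and solving for the CBP-201 non-AD rate, with AD at 26.1% v 37.5%:

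- placebo non-AD 30%: CBP-201 40.8%, hidden excess 10.8 points (about 18 of 170 subjects)
- placebo non-AD 40%: CBP-201 49.3%, hidden excess 9.3 points (about 16)
- placebo non-AD 50%: CBP-201 57.7%, hidden excess 7.7 points (about 13)

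With AD at 15% v an assumed 25% to 40%, the hidden excess is 5.9 to 20.6 points.

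**4. Where the effect disappears.** With AD at 15% in both arms, equal totals hide 0 points. A 50% v 40% excess would then show as 57.5% v 49.0%, a difference of 8.5 points. Independence also matters. If every subject with a flare also had another TEAE, the totals would be 50% v 40% and nothing would be masked. If no subject had both, they would be 50 + 26.1 = 76.1% v 40 + 37.5 = 77.5%.

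**5. Can the AD-free total be recovered?** Not from the overall row and the AD row, because the overlap is unknown. On placebo, a total of 62.5% with AD at 37.5% allows any non-AD rate from 62.5 − 37.5 = 25.0% to 62.5%. On CBP-201, 63.1% with AD at 26.1% allows 37.0% to 63.1%. Other preferred-term rows narrow this but cannot be added up, since one subject can appear in several. The recurrence analysis in SAP 7.4.4 counts subjects who flared, not whether they also had another event.

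**6. What the separate AD-recurrence output is.** SAP 7.5.2 promises a tabulation without saying whether it is a by-arm summary or a listing. SAP 7.1 and 7.2.1 use the word for output carrying subject numbers and unimputed dates, which suggests a listing. Recording by site of attack may also turn one flare into several AE records, which affects event counts.

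**The case against.** The strongest reply is that the plan already separates AD. Every TEAE category is broken down by SOC and preferred term, AD recurrence-related AEs are a named output, and recurrence is compared between arms. Protocol 12.8 lists discontinuation TEAEs by patient, so that count could be made by hand. An excess in a particular term would be visible even if the totals were level. This stands, and it confines the problem to the subject-level totals. A reader might infer that AD is never separated or that the plan conceals harm; the documents do not support either.

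A reader might also infer that each flare enters every total. It does not. Drug-related requires a rating of related, possibly related or indeterminable, and the causality criteria in SAP 4.2.2 name preexisting disease as an alternative explanation. Grade 3-5 and interruption have their own criteria. For discontinuation, the action must be in response to the AE. Whether a stop triggered by systemic rescue is coded that way depends on how the site completes the eCRF, which the documents do not show. Systemic rescue is also meant to follow at least 7 days of topical treatment.

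Finally, safety is described rather than tested, and protocol 10.1.3 and 10.4.1 require worsening of a preexisting condition to be an AE. The overall row therefore reports what it defines. That is right, and it is why the existing rows should stay.

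**Conclusion.** The point holds in a limited form. Flares needing rescue are both an efficacy endpoint and AEs, no TEAE total excludes them, and no planned summary gives the subject-level incidence without them. If flares are more common on placebo, the crude Stage 1 comparison of overall TEAEs favours CBP-201; the AE-discontinuation comparison may do so too.

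The size is not established. The illustration of 63.1% v 62.5% for a true 10-point excess rests on assumed non-AD rates, independence, and AD rates from a study with 8 placebo patients. A higher placebo flare rate is plausible, since the trial itself expects 27% v 9% response, but it is not demonstrated.

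Two further inferences go too far. One is that the safety conclusion should be read only from AD-free rows; AD worsening could itself be treatment-related, and the protocol defines it as an AE. The other is that the same distortion affects SS2 and SS3; those sets are reported by CBP-201 regimen with no concurrent placebo arm. The primary endpoint is little affected, because intercurrent events 1, 3 and 4 all count as non-response.

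**What to change.** In SAP 7.5.2:

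- Keep all existing rows.
- For SS1, by arm, add supplementary rows for any TEAE and for TEAEs leading to treatment discontinuation, excluding AD recurrence-related AEs. Grade 3-5 and interruption rows are optional.
- Use the set of AD recurrence-related AEs that the SAP already identifies, so no new choice of terms is needed.
- Report the AD recurrence-related AEs as a by-arm summary (subjects and events), not only as a listing.
- State that both sets of rows are interpreted side by side. Do not replace the all-TEAE rows or treat AD worsening as efficacy only.

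SAP section 6 dates the blinded data review for the primary analysis to 19 September 2022. If Stage 1 has since been unblinded, label the new rows as added afterwards.

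The cost is one SAP paragraph and a few table rows, with no new data. The downside is two sets of totals to explain.

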1.1. Study Design Diagram

[figure not shown]

Figure 1: Study Design Diagram

Note:

1. The subjects will receive a loading dose of the study drug (investigational product/placebo) on D1 at a dose of 600 mg (4 ml);
2. Response is defined as a 50% or more decrease in the EASI score;
3. In order to maintain the injection every 2 weeks blind, when not receiving CBP-201, the subjects will receive an injection of placebo 2 ml once every 4 weeks until W52.
4. If subjects in group C and group D have not achieved EASI-50 in two continuous pre-administration treatment assessments, they will be assigned to group E to be treated with subcutaneous injection of CBP-201 300 mg every 2 weeks from the visit when EASI-50 is not achieved for the second time to W50.

1.2. Study Flow Chart

Table 1.1 Screening Period + Stage 1 Treatment Period Flow

Assessment	Screening period D-28~D-1	Stage 1 treatment period									
		D1 Pre-dose	D1 Post-dose	D15 W2 (±3d)	D29 W4 (±3d)	D43 W6 (±3d)	D57 W8 (±3d)	D71 W10 (±3d)	D85 W12 (±3d)	D99 W14 (±3d)	D113 W16 pre-dose (±3d)
Informed consent ¹	√										
Demographic characteristics	√										
Medical history ¹	√										
Inclusion and exclusion criteria ¹	√	√									
Height	√										
Weight	√	√			√		√		√		√
Physical examination ²	√										√
Vital signs ³	√	√	√	√	√	√	√	√	√	√	√
12-lead ECG	√	√									√
Chest X-ray	√										
Eye examination ⁴	√	√		√	√	√	√	√	√	√	√
Hepatitis and HIV screening ⁵	√										
Safety laboratory tests ⁶	√	√		√	√		√				√
Pregnancy test ⁷	√	√			√		√		√		√
FSH test ⁸	√										
PK blood sample ⁹		√		√	√		√		√		√
PD blood sample ⁹		√		√	√		√		√		√
ADA ¹⁰		√		√	√		√		√		√
Investigator's efficacy assessment ¹¹	√	√		√	√		√		√		√
Patient reported outcomes ¹²	√	√		√	√	√	√	√	√	√	√
PP-NRS ¹³	√	√		√	√	√	√	√	√	√	√
Randomization ¹⁴		√									√
SC administration of study drug ¹⁵			√	√	√	√	√	√	√	√	√
Injection site assessment ¹⁶			√	√	√	√	√	√	√	√	√
AE ¹⁷	√	√	√	√	√	√	√	√	√	√	√
Prior and concomitant medication/treatment	√	√	√	√	√	√	√	√	√	√	√

Table 1.2 Stage 2 Maintenance Treatment Period + Follow-up Period Flow (Including Unscheduled Visit + Early Termination)

Assessment	Stage 2 maintenance treatment period																		Follow-up visit		Unscheduled visit ¹⁷	ET ¹ +7d
	D113 W16 post-dose (±3d)	D12 7 W1 8 ±3d	D14 1 W2 0 ±3d	D15 5 W2 2 ±3d	D16 9 W24 ±3d	D18 3 W26 ±3d	D19 7 W28 ±3d	D21 1 W30 ±3d	D22 5 W32 ±3d	D23 9 W34 ±3d	D25 3 W36 ±3d	D26 7 W38 ±3d	D28 1 W40 ±3d	D29 5 W42 ±3d	D30 9 W44 ±3d	D32 3 W46 ±3d	D33 7 W48 ±3d	D35 1 W50 ±3d	D36 5 EO T W52 ±3d	D393 W56 ±3d	EOS D421 W60 ±3d	
																			D393 W56 ±3d	EOS D421 W60 ±3d		
Weight			✓		✓		✓		✓		✓		✓		✓		✓		✓	✓	✓	✓
Physical examination ²																			✓	✓	✓	✓
Vital signs ³	✓	✓	✓	✓	✓	✓	✓	✓	✓	✓	✓	✓	✓	✓	✓	✓	✓	✓	✓	✓	✓	✓
12-lead ECG																			✓	✓	✓	✓
Eye examination ⁴		✓	✓	✓	✓	✓	✓	✓	✓	✓	✓	✓	✓	✓	✓	✓	✓	✓	✓	✓	✓	✓
Safety laboratory tests ⁶					✓				✓									✓		✓	✓	✓
Pregnancy test ⁷			✓		✓		✓		✓		✓		✓		✓		✓		✓	✓	✓	✓
PK blood sample ⁹		✓		✓		✓		✓		✓		✓		✓		✓		✓	✓	✓	✓	✓
PD blood sample ⁹		✓		✓		✓		✓		✓		✓		✓		✓		✓	✓	✓	✓	✓
ADA ¹⁰		✓		✓		✓		✓		✓		✓		✓		✓		✓	✓	✓	✓	✓
Investigator's efficacy assessment ¹¹		✓		✓		✓		✓		✓		✓		✓		✓		✓	✓	✓	✓	✓
Patient reported outcomes ¹²		✓	✓	✓	✓	✓	✓	✓	✓	✓	✓	✓	✓	✓	✓	✓	✓	✓	✓	✓	✓	✓
PP-NRS ¹³		✓	✓	✓	✓	✓	✓	✓	✓	✓	✓	✓	✓	✓	✓	✓	✓	✓	✓	✓	✓	✓
SC administration of study drug ¹⁵	✓	✓	✓	✓	✓	✓	✓	✓	✓	✓	✓	✓	✓	✓	✓	✓	✓	✓				
Injection site assessment ¹⁶	✓	✓	✓	✓	✓	✓	✓	✓	✓	✓	✓	✓	✓	✓	✓	✓	✓	✓	✓	✓	✓	✓
AE ¹⁷	✓	✓	✓	✓	✓	✓	✓	✓	✓	✓	✓	✓	✓	✓	✓	✓	✓	✓	✓	✓	✓	✓
Concomitant medication/treatment	✓	✓	✓	✓	✓	✓	✓	✓	✓	✓	✓	✓	✓	✓	✓	✓	✓	✓	✓	✓	✓	✓

Abbreviations: AD=atopic dermatitis; ADA=anti-drug antibody; AE=adverse event; DLQI=Dermatology Life Quality Index; EASI=eczema Area and Severity Index; ECG=electrocardiogram; EOS=end of study; EOT=end of treatment; ET: early termination; FCBP=female of childbearing potential; HIV=human immunodeficiency virus; HR=heart rate; ICF=informed consent form; IGA=validated investigator global assessment; PD=pharmacodynamics; PK=pharmacokinetics; PP-NRS=Peak Pruritus Numerical Rating Scale; POEM=Patient Oriented Eczema Measure; SAE=serious adverse event; SC=subcutaneous injection; SCORAD=Scoring Atopic Dermatitis Index; VS=vital signs.

Footnotes

1. Before D1 administration of study drug, it must be reconfirmed that the subject has signed the ICF and is eligible for selection. The medical history should also be reviewed before D1 administration.
2. A complete physical examination (PE) is required at screening, W16, W52, EOS/ET and unscheduled visits. The items included are as follows: general appearance, skin, eyes/ears/nose/throat, head and neck, cardiovascular system, respiratory system, abdomen, limbs, lymph nodes, musculoskeletal and nervous systems. Unless it is necessary to assess the status of AD involvement, there is no need to perform rectal or genital examinations. Priority physical examinations can be performed at visits where PE are not scheduled. Attention should be paid to the AD involvement areas and assessment of any AE.
3. Vital signs (VS) include body temperature, respiratory rate, blood pressure, and heart rate. In the Stage 1 treatment period, on D1 and at W2 and W4, VS should be monitored every hour (± 10 min) pre-dose and during the 2-hour monitoring period post-dose; from W6 to W14, VS should be monitored pre-dose and 30 min (± 10 min) post-dose. In the Stage 2 maintenance treatment period, VS should be monitored every hour (± 10 min) pre-dose and during the 2-hour monitoring period post-dose at W16, W18, and W20; from W22 to W50, VS should be monitored pre-dose and 30 (± 10 min) min post-dose. During the follow-up period, VS should be monitored at each visit.
4. Eye examination: At each visit, the investigator must assess whether the subject has any eye discomfort, such as redness, itching, photophobia and abnormal discharge, as well as related signs/symptoms, such as conjunctival hyperemia and exudate. If these discomforts are considered to be related to conjunctivitis or keratitis or any uncertain diagnosis, an ophthalmologist should conduct further assessment and give appropriate treatment.
5. Hepatitis screening: Hepatitis B surface antigen, core antibody, HBV-DNA and hepatitis C antibody, HCV-RNA.
6. Safety laboratory tests: Including hematology, blood biochemistry and urinalysis. See [Table 9.1](#) for safety laboratory tests; the test results within 7 days before baseline can be accepted for D1, and there is no need to repeat the test. If the test is performed on the treatment day, samples need to be collected for laboratory tests before administration.
7. For all female subjects of childbearing potential (FCBP), a blood pregnancy test should be performed during the screening period and a urine pregnancy test should be performed on D1 and every 4 weeks thereafter. The test results within 7 days before baseline can be accepted for D1, and there is no need to repeat the test.
8. FSH test: Only for menopausal female subjects; subjects who can provide FSH test results before the screening visit do not need to repeat the test.
9. The trough-concentration (pre-dose) PK/PD samples should be collected (D1, W2, W4 and every 4 weeks thereafter, until W16; once every 8 weeks at W20 and thereafter, until W52); PK/PD samples should also be collected at the early termination visit and follow-up period (W60); among them, blood samples will not

be collected for PD parameter—peripheral blood eosinophils at W12, W20, W28, W36, W44, W52; the collection date and time of each sample will be recorded.

10. If ADA is positive, NAb analysis is also required.
11. Investigator assessments before administration include EASI, IGA, BSA, and SCORAD. If possible, the investigator assessment of the individual subject should be performed by the same person.
12. Patient reported outcomes includes DLQI and POEM, which are assessed once a week. The investigator will dispense the subject diary at each visit and collect DLQI and POEM data of that day, and the data among two visits will be assessed by the subjects themselves and recorded in the subject diary. Old diaries dispensed last time will be collected at the next visit and the new ones will be dispensed. DLQI score will only be assessed among subjects ≥ 16 years.
13. The PP-NRS (Daily Pruritus Diary) will be distributed at the beginning of the screening and will be reviewed by the study staff at baseline (D1). Baseline PP-NRS must be completed during the screening period, and subjects should complete the daily records within 7 days before the baseline visit (*in these 7 days, the scores of at least 4 days are required for the calculation of the baseline average score. If the patient's reporting days are less than 4 days in the 7 days before the planned date of randomization, randomization should be postponed until the requirements are met, but it is not allowed to exceed the maximum screening period of 28 days*) to determine the baseline severity of pruritus before treatment. During the study period, subjects should record the PP-NRS score of the maximum pruritus intensity in the past 24 hours in the subject's daily diary.
14. Randomization: Two randomizations will be conducted during this study:
 - First time: After subjects complete the screening period and meet the inclusion criteria after D1 pre-dose assessment, they can be randomized to Group A (CBP-201 300 mg Q2W) or Group B (placebo Q2W) in a 2:1 ratio before D1 administration;
 - Second time: Subjects who are assessed to have achieved EASI-50 before W16 administration will be randomized to Group C (CBP-201 300 mg Q2W) or Group D (CBP-201 300 mg Q4W) in a ratio of 1:1.
15. Unless otherwise stated, all study assessments and examinations should be completed before administration of study drug at each visit. The injection site should be rotated: the abdomen (avoid the area near the umbilicus), the outer thigh, and the upper arm (outer or posterior lateral).
16. The assessment of the injection site will be performed using the injection site response evaluation criteria ([Appendix H](#)) provided to each study site. A clinically significant response judged by the investigator will be reported as an AE. At the visit of dosing day, the previous injection site should be assessed before administration (except D1), and the new injection site should be assessed before the subject leaves the study site; only the previous injection site is assessed at the visits when no drug is administered.
17. AEs (the AEs collected before the signing of the ICF to D1 are recorded as pre-treatment adverse events [PTAE]) and SAEs will be collected from the signing of the ICF. AEs and AEs of special interest (AESI) will be collected at each study visit.
18. Unscheduled visits (UV) or the ET visit can be conducted at any time. UV can be conducted for reasons such as AE or disease progression assessment. The investigator can decide which assessments are suitable for an UV, but at least VS and PE (including injection site assessment) should be performed, and the subject should be asked whether any AE has occurred and whether there are new concomitant medications or treatments. If a subject has ET for any reason, an

ET visit should be completed within 7 days after ET to determine the cause of ET, and such assessments should be conducted under the assumption that subject is willing to return to the study site to undergo the end-of-study assessment procedures. It should be noted that ET subjects should also try their best to complete the 8-week follow-up visit after the last dose of study drug.

2. Table of Contents

Protocol Signature Page—Principal Investigator	2
Protocol Signature Page—Sponsor.....	3
Protocol Signature Page—Statistical Analysis Unit.....	4
Protocol Signature Page—Statistical Analysis Unit (Pharmacokinetics)	5
Protocol Signature Page—Other Study Centers	6
1. Protocol Synopsis.....	9
1.1. Study Design Diagram	23
1.2. Study Flow Chart	24
2. Table of Contents.....	29
2.1. List of Tables	32
3. List of Abbreviations and Definitions of Terms	33
4. Introduction	36
4.1. Background.....	36
4.2. Physical, Chemical and Pharmacological Properties	37
4.3. Preclinical Studies	37
4.4. Clinical Studies.....	38
4.5. Other Safety Considerations	43
4.6. Study Rationale	44
5. Study Objectives	47
5.1. Primary Objective.....	47
5.2. Secondary Objectives.....	47
6. Study Plan	48
6.1. Overall Study Design and Plan	48
6.2. Study Steps.....	49
